## 2.4 Trials registration

Application in progress

## **3. Research Financing**

Total cost including any reimbursement of researchers:

The only direct cost of the study is the working time of the researchers, which is included in the calculation of direct working time. The University of Tartu funds [name] as a visiting professor. [name] is paid as a junior scientist by the University of Tartu. Master's and Bachelor's students are not funded. The patient's measurements (body weight, height, and simple muscle mass measurements) are not associated with any cost. The full-body DEXA scans are paid for from [name] personal research grant: these funds are held at the University of Tartu. Small unexpected expenses can also be covered by [name] personal research grant. Patients in the study will not receive any benefits in kind / financial compensation.

## **4. Brief overview of previous research on the same topic**

Muscle mass is a common criterion for the assessment of malnutrition and sarcopenia (1). However, evaluation of muscle mass with gold-standard methods is often challenging in healthcare settings due to their high cost, lack of portability, and impracticality (2). Anthropometric measurements such as calf circumference (CC) are cost-effective, simple

alternative techniques that can be performed to estimate muscle mass in clinical settings (3,4).

Earlier Asian validation studies affirmed the good diagnostic performance of CC for detecting low appendicular lean mass and sarcopenia (5,6). The Asian Working Group for Sarcopenia (AWGS) 2019 consensus recommended the addition of calf circumference in order to improve the sensitivity of sarcopenia screening (SARC-F)(7). Compared with SARC-F, Calf circumference (CC) had better diagnostic performance but its performance decreased in those with sarcopenic obesity (especially in women)(8).

The Global Leadership Initiative on Malnutrition (GLIM) also supports the use of calf circumference or mid-upper arm circumference for assessment of skeletal muscle mass when DEXA, BIA or CT are not available (3). A cohort study validated the use of GLIM criteria for malnutrition diagnosis by comparing CC and MUAC measurements against the Subjective Global Assessment (SGA) in hospitalized patients. Both measures showed strong accuracy for detecting malnutrition (9). However, CC's diagnostic performance decreases in patients with a  $BMI \geq 30 \text{ kg/m}^2$ , particularly women. In patients with obesity, study showed weaker correlations between CC and fat-free mass index (FFMI) as a measure of muscle mass (10).

This highlights the need for future research to define new strategies and threshold corrections for accurate muscle mass assessment in clinical practice for patients with obesity.

2. Fayh APT, de Sousa IM, Gonzalez MC. New insights on how and where to measure muscle mass. *Curr Opin Support Palliat Care.* 2020;14(4):316–23.

## **5. Purpose, summary and justification of the proposed research**

The issue of obesity for calf circumference (CC) has been addressed in various studies. Calf skinfold thickness has been suggested for adjusting CC in patients with obesity, but the method has limitations, can lead to errors and it is time-consuming. The NHANES study in the U.S. showed that adjusting calf circumference for BMI helps to detect age- associated, and sex-specific lower values of calf circumference (1). However, few studies have validated BMI-adjusted CC in hospitalized patients (2).

The aim of the study is to find out whether calf circumference (CC), corrected with mid-upper arm circumference (MUAC), will provide more accurate estimate of muscle mass in patients with obesity. Mid-upper arm circumference (MUAC) is more representative of body fat mass than of muscle mass in patients with obesity, especially in women (3). Therefore, there is a reason to believe that MUAC will improve the accuracy of calf circumference as a muscle mass measure by adjusting for the influence of fat.

The research hypothesizes that calf circumference corrected with mid-upper arm circumference is more accurate than just calf circumference at detecting reduced muscle mass in patients with obesity. In case the hypothesis proves true, corrected calf circumference measurement will have the potential to be an easy and simple approach for estimating muscle mass in patients with obesity in clinical or limited settings.

3. Kurik G, et al. Poor correlation between calf circumference and muscle mass in patients with obesity. *Clin Nutr ESPEN.* 2024;63:1121.

## **6. Timescale of research**

It is planned that the study will run from January 2025 until June 2026. The initial data collection will end on the 31st March 2025.

## **7. Detailed description of the research participants and their recruitment**

All patients of the internal clinic of the University of Tartu Hospital who are to have a DEXA scan can be included in the study. The goal is to recruit a maximum of 150 eligible adult (older than 18 years old) patients until 31.03.2025.

Patients isolating because of an infectious disease, with pregnancy, lactation, acute sepsis, severe dehydration or volume overload and inability to follow study procedures are excluded.

The patient is contacted in person and given an information sheet (in Estonian or Russian as appropriate). The patient will be informed about the structure of the study. If the patient agrees to participate, they will sign the consent form. Participation in the study is voluntary. The patient will not be included in the study until they have read the patient consent form, understood the content of the study, received answers to any questions they may have, and voluntarily signed two copies of the written consent form (one for the patient and one for retention at the University of Tartu.)

## **8. Detailed description of the research methodology**

The patient's demographic data including age, sex, primary diagnosis, and diagnoses of comorbidities are found by the investigator in the medical history (eHL). The researcher codes the current main diagnosis and its severity: we use the World Health Organization's ICD-11 classification ([icd.who.int/browse11/l-m/en](http://icd.who.int/browse11/l-m/en)) and a three-point scale where 1 is mild and 3 is severe.

The patient will be interviewed for changes in body weight and food intake. Anthropometric measurements will be recorded, including height, weight, body mass index (BMI), mid upper arm circumference, calf circumference, and waist circumference.

The accurate muscle mass measurement will be done using total body DEXA scan, that was already ordered for other purposes. Bone mineral density (BMD) from DEXA scan will be recorded. This allows us to see if calf circumference can be used for estimating bone mineral density. Patients will be followed up one year after data collection. Follow up will involve calling the patients and asking them questions from SarQoL (sarcopenia quality of life questionnaire)

Calf circumference will be measured using non-elastic tape at the widest part of the dominant calf in the seated position with the weight evenly distributed on both feet (1). Mid upper arm circumference will be measured at the midpoint between the acromial surface of the scapula and the olecranon process of the elbow over the dominant arm when bent at 90 degrees. Waist circumference will be measured using measuring tape 2.5 cm above the umbilicus in standing position. Waist circumference is used to define obesity as it is a marker of abdominal obesity (2). We aim to keep the interview no longer than 10 minutes.

Demographic and anthropometric data will be analyzed using descriptive statistics. The sensitivity, specificity of muscle mass measurements will be calculated. Corrected calf circumference will be compared to DEXA (gold standard diagnostic tool) and new cutoffs will be defined by using Receiver operating characteristic curves. Statistical analyses will be performed using R.

1. Rose Berlin Piodena-Aportadera M, Lau S, Chew J, et al. Calf circumference measurement protocols for sarcopenia screening: differences in agreement, convergent validity, and diagnostic performance. *Ann Geriatr Med Res.* 2022;26:215–24.

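### Does it matter for the results that the DEXA scan is described as already ordered, yet is also charged to a research grant?

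*Protocol*

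**What the plan says.** Four statements in the protocol bear on the DEXA scan.

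- Section 8 (methodology) gives its origin. Muscle mass is measured by a "total body DEXA scan, that was already ordered for other purposes".
- Section 3 (financing) gives its payer: "The full-body DEXA scans are paid for from" a researcher's personal grant held at the University. The same paragraph also states: "The only direct cost of the study is the working time of the researchers".
- Section 7 (participants) makes a booked scan the entry condition. Patients of the internal clinic "who are to have a DEXA scan can be included in the study". It does not say whether the scan is total-body or regional, or who orders it.
- Section 8 also gives the scan its role in the analysis: "Corrected calf circumference will be compared to DEXA (gold standard diagnostic tool"). The new cutoffs come from ROC curves, and sensitivity and specificity are to be calculated.

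The only size given is a ceiling, with no calculation behind it: "The goal is to recruit a maximum of 150 eligible adult" patients.

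**The concern.** DEXA is the reference standard for the whole study, so its status should be beyond doubt. Read together, sections 3, 7 and 8 seem to describe two different studies. In one, the investigators take measurements alongside a scan that would have happened anyway. In the other, they buy a total-body scan for patients booked for some other DEXA examination.

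Three things could hang on which is true.

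1. **Completeness of the reference measure.** A regional scan gives no whole-body or appendicular lean mass. A patient booked only for a regional scan meets the wording of section 7, but could not enter the accuracy analysis unless a total-body scan were added.
2. **The patients behind the cutoffs.** People already referred for total-body DEXA may differ from DEXA patients in general, and sensitivity, specificity and ROC cutoffs can vary with case mix.
3. **Study-initiated imaging.** If the scan is added for research it is a study procedure, and section 8 does not present it as one.

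**Working it through.** The protocol states no figure that depends on this point, so there is nothing to reproduce. The check is a comparison of the statements, followed by one line of arithmetic.

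**Step 1. Do the cost sentences in section 3 agree?** No. One says working time is the only direct cost; the other has a grant paying for scans. This conflict stands on any reading, but it concerns the budget alone. It does not touch eligibility, measurement or analysis.

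**Step 2. Does section 3 contradict section 8?** Not strictly. Section 8 says the scan was ordered for other purposes; it does not say those purposes are routine care. Ordering and paying are different facts. A scan ordered for another grant-funded project, for example, would satisfy both sentences. The protocol does not say this is what happened, so the link is unexplained, but neither sentence has to be false.

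**Step 3. Which type of scan is the reference?** Section 8 says total-body and section 3 says full-body. Only section 7 leaves the type open, and it is the general statement; section 8 is the specific one. No section describes using a regional scan as the reference, or enrolling a patient without a total-body scan.

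**Step 4. Who has a reference value under each reading?**

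| Reading | Total-body scan for every enrolled patient? |
|---|---|
| A. Total-body scan already ordered; the study uses it | Yes |
| B. Patient booked for another DEXA; total-body scan added at the grant's cost | Yes |
| C. Patient enrolled on a regional scan, nothing added | No, but no section describes this |

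**Step 5. Size.** Let m be the share of enrolled patients with only a regional scan. At the ceiling of 150, the number with a reference value is 150 × (1 − m).

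- Readings A and B: m = 0, giving 150 × 1 = 150.
- Reading C, with m assumed because the protocol gives no value: m = 0.2 gives 150 × 0.8 = 120; m = 0.5 gives 150 × 0.5 = 75.

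The losses of 30 and 75 arise only in reading C. They follow from the assumed m and from nothing in the protocol.

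**Step 6. Does the analysis differ between A and B?** No. In both, corrected calf circumference is compared with total-body DEXA in clinic patients who were due a DEXA scan. The case mix may differ, but section 8 already collects primary diagnosis, comorbidities and a coded severity for each patient, and summarises demographic data descriptively. The spectrum behind the cutoffs can therefore be reported whichever reading is true.

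**The case for a change.** The strongest case for acting is that the origin of the reference test, the entry condition and the list of study procedures belong in the protocol and cannot be left to an analysis plan. The statements are in the text, none is explained by a removed name, and a few words would reconcile them. Section 7 is looser than section 8, and a recruiter reading section 7 alone could enrol someone whose scan is regional.

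Part of this stands. Section 3 is inconsistent about cost, the origin of the scan is not explained, and the section 7 wording could be tighter. A short query to the investigators would be reasonable housekeeping.

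The consequences do not follow, however. A recruiter works to the whole protocol, and section 8 names the scan that is needed. The case-mix argument is sound in general, but it concerns how the sample is described and changes neither the comparison nor the method for setting cutoffs. On imaging exposure, section 9 deals with confidentiality and data storage and is silent on scans; silence is not a statement that there are none. The information sheet and consent form are listed in section 11.2 but are not available here, so what participants are told about the scan cannot be judged.

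Narrowing the entry criterion might not be free either. If total-body scans are seldom ordered and none are added by the study, the pool could shrink, with recruitment due to end on 31 March 2025. The protocol gives no figure for that.

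**Conclusion.** The inconsistency is real but clerical: a wrong or incomplete cost sentence in section 3, an unexplained link between funding in section 3 and ordering in section 8, and a loose phrase in section 7. Followed as written, the plan measures muscle mass by total-body DEXA in every enrolled patient and compares corrected calf circumference with it. The expected loss of reference values is 0 of at most 150 under either reading that the text supports, and no stated figure changes.

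This rests on two assumptions: that section 8's total-body requirement governs who is enrolled, as its specific wording implies, and that the removed consent documents describe the scan correctly. If the second failed, the matter would be one for the ethics file and would not alter the statistical plan. No change to the plan follows.

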#### **10. Information about previous or similar projects undertaken elsewhere**

The researchers have been a part of a similar project conducted at Tartu University Hospital from December 2023 to May 2024. The aim of the project was to establish whether a limb circumference, namely calf circumference (CC) or mid-upper arm circumference (MUAC), has the potential to become the preferred muscle mass assessment method of a standardised, globally accessible GLIM protocol. In both males and females there was good correlation between CC and fat-free mass index (FFMI) in patients without obesity. The correlation between CC and FFMI was weaker in patients with obesity and almost absent in females with obesity. The researchers have not encountered any problems. This experience helps to improve confidence in the feasibility of the new study given a similar time frame.

After we complete the current study, we also aim to look at this previous dataset to find out whether the new corrections work for the patients with obesity. This will validate the results of the study.

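### Section 8 sets new ROC cutoffs and, on the natural reading, scores accuracy in the same cohort of at most 150, so the reported sensitivity and specificity will be optimistic

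*Protocol*

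**What the plan says.** The hypothesis in Section 5 is that "calf circumference corrected with mid-upper arm circumference is more accurate than just calf circumference at detecting reduced muscle mass in patients with obesity". CC is calf circumference and MUAC is mid-upper arm circumference. The rationale is that "MUAC will improve the accuracy of calf circumference as a muscle mass measure by adjusting for the influence of fat".

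Section 7 does not restrict entry to obesity: "All patients of the internal clinic of the University of Tartu Hospital who are to have a DEXA scan can be included". It sets a ceiling on numbers: "The goal is to recruit a maximum of 150 eligible adult" patients.

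Section 8 gives the analysis in outline. "The sensitivity, specificity of muscle mass measurements will be calculated", and then: "Corrected calf circumference will be compared to DEXA (gold standard diagnostic tool) and new cutoffs will be defined by using Receiver operating characteristic curves". No other sample, data split or resampling is described for this step, and no correction formula is given.

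Section 10 adds that, once the study is finished, "we also aim to look at this previous dataset to find out whether the new corrections work for the patients with obesity". That dataset comes from a project at the same hospital between December 2023 and May 2024. The protocol calls this step validation.

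**The concern.** A cutoff chosen because it performs best in a sample performs less well in new patients. Sensitivity and specificity scored in the sample that produced the cutoff are therefore too favourable. The fewer the patients, and above all the fewer the cases of low muscle mass, the larger the excess. Here the hypothesis concerns only part of a cohort that is itself capped at 150.

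A second question is whether the comparison with plain CC is affected. Cutoff optimism largely cancels if both measures get new cutoffs. It does not cancel if plain CC is judged at existing cutoffs. If the weight given to MUAC is also estimated in this cohort, corrected CC has an extra fitted step and tends to look better even when MUAC contributes nothing.

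Section 5 draws a practical conclusion from the result: "In case the hypothesis proves true, corrected calf circumference measurement will have the potential to be an easy and simple approach". Cutoffs and accuracy figures taken from this study could be used by others.

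**Working it through.** **The plan's own figure.** The 150 is a ceiling with no alpha, power, precision or expected accuracy behind it, so there is nothing to reproduce.

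**Inputs.** From the protocol: at most 150 patients, obese share not stated. Assumed, because the protocol gives no figure: 20% with low muscle mass; correlation r of CC with muscle 0.3 to 0.5; correlation of CC with MUAC 0.6; cutoffs by the Youden index; n from 45 (30% of 150 = 45) to 150. At 20%, that is 9 cases at n=45 and 30 at n=150.

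**Definitions.** Youden index J = sensitivity + specificity − 1. Optimism = J in the sample that chose the cutoff, minus J of the same cutoff in new patients. AUC gain = AUC(corrected CC) − AUC(plain CC). Each setting used 1,200 simulated studies, with each rule scored on 4,000 new patients.

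**Step 1: cutoff optimism, plain CC (r=0.3, then r=0.5).**
- n=45: 0.38 − 0.18 = 0.20 and 0.51 − 0.32 = 0.19.
- n=150: 0.30 − 0.19 = 0.11 and 0.43 − 0.34 = 0.09.

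A correction fixed in advance, CC minus MUAC, has the same optimism: 0.18 to 0.21 at n=45 and 0.08 to 0.11 at n=150.

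**Step 2: the same question under a different model.** For a single normally distributed marker with true AUC 0.75, the separation is d = √2 × Φ⁻¹(0.75) = 0.954. The best J that any cutoff can reach is 2Φ(d/2) − 1 = 0.367. With 30% cases:
- n=150, 45 cases: apparent 0.425, true 0.349, optimism 0.076.
- n=45, 14 cases: apparent 0.480, true 0.335, optimism 0.145.

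Both apparent values exceed the attainable maximum. Over true AUC 0.65 to 0.85 and 15 to 30% cases, optimism is 0.06 to 0.12 at n=150 and 0.13 to 0.21 at n=45.

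**Step 3: the gain over plain CC.** With a correction fixed in advance, the AUC gain is unbiased to within 0.005. If the MUAC weight is fitted in the same cohort, the result depends on what MUAC carries. MUAC adds nothing to CC when its correlation with muscle equals 0.6r, since 0.6r − 0.6 × r = 0. It is a pure marker of fat when that correlation is 0.

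| MUAC–muscle correlation | n=45 apparent | n=45 true | n=150 apparent | n=150 true |
|---|---|---|---|---|
| 0.6r (adds nothing) | +0.02 to +0.043 | −0.024 to −0.043 | +0.006 to +0.012 | −0.006 to −0.013 |
| 0.3r (partly informative) | +0.039 to +0.050 | −0.032 to −0.004 | +0.020 to +0.022 | −0.001 to +0.012 |
| 0 (pure fat) | +0.070 to +0.078 | −0.001 to +0.044 | +0.044 to +0.067 | +0.029 to +0.059 |

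Where MUAC adds nothing, corrected CC still looks better in 66 to 77% of studies. Where MUAC marks fat, most of the gain at n=150 is real.

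If plain CC keeps an outside cutoff, it has no cutoff optimism of its own. The Step 1 excess for corrected CC then enters the comparison of sensitivity and specificity in full.

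**Step 4: what the Section 10 check can do.** With an assumed 45 patients in the earlier dataset and the rule carried over unchanged, the mean AUC gain there is −0.025 to −0.042 when MUAC adds nothing and −0.003 to +0.048 when it marks fat. Both are close to the true values, so the check is useful if the rule is not altered.

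**The case against.** The strongest reply is that Section 8 is a short outline, that deriving ROC cutoffs is a normal first step, and that an optimism correction may stand in an analysis plan not seen here. That is fair. For the same reason the missing correction formula is not a flaw in itself. But the step as described gives figures that are too favourable, and a sentence or a cross-reference removes the doubt.

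Four stronger readings are tempting, and the protocol does not support them.
- *That no validation is planned.* Section 10 plans one and poses it as an open question, so its closing remark about validation need not be taken as presuming success. The check remains an aim for after the study, names the corrections but not the cutoffs, and does not say that the rule is frozen.
- *That the correction is certainly fitted in this cohort.* This is inferred from the wording of "we also aim to look at this previous dataset to find out whether the new corrections work for the patients with obesity". A fixed ratio or difference is equally open.
- *That the gain over plain CC is spurious.* If MUAC marks fat, as Section 5 expects, most of it is real at n=150. If MUAC adds nothing, the false gain at n=150 is only 0.006 to 0.012 in AUC.
- *That Section 8 says accuracy is read at the new cutoffs, or that plain CC gets a new one.* It says neither. The first is only the natural reading, and the second is unknown.

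It is also true that every input to the sizes is assumed, that Section 8 names ROC curves but not AUC as an outcome, and that Section 5 speaks only of potential use. The range r 0.3 to 0.5 leaves out the near-absent correlation that Section 10 reports in women with obesity. In Step 2, cutoff optimism was larger at lower true AUC.

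**Conclusion.** The point holds in a limited form. If sensitivity and specificity are read at the new cutoffs in the patients who produced them, their sum is too high by about 0.10 at n=150 and about 0.2 at n=45. The direction does not depend on the correction formula, and two different models agree on the rough size. The sizes rest on assumed prevalence, correlations, Youden cutoffs and obese share.

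Inflation of the gain over plain CC is conditional. It needs either a correction fitted in this cohort or existing cutoffs kept for plain CC, and the protocol states neither. The Section 10 check answers the concern in part. The point is worth acting on because the change is cheap, but it is not a reason to doubt the study's design.

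**What to change.** In Section 8, add (or refer to an analysis plan that says):

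> In patients with obesity, AUC, sensitivity and specificity of corrected and plain CC, and their differences, will be reported with a bootstrap optimism correction that repeats every fitted step (correction and cutoff) for both measures. Uncorrected figures will be labelled apparent. Corrected sensitivity and specificity may remain somewhat optimistic in a small subgroup.

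The last sentence is needed. In 12 simulated settings (n=45 and 150) the bootstrap brought the AUC gain within 0.015 of the true value, and the difference in J between the two measures within about 0.025. J itself stayed 0.06 to 0.10 too high at n=45 and 0.02 to 0.04 too high at n=150. At n=45 that is roughly a third to a half of the bias (0.06/0.18 = 0.33; 0.10/0.21 = 0.48).

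In Section 10, replace the closing sentence with:

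> The correction formula, and the cutoffs where the reference measure of the earlier dataset allows, will be fixed and dated before they are applied unchanged to that dataset. This is a same-centre temporal validation; the correlations of plain CC with muscle mass in that dataset are already known.

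The proviso on cutoffs is there because Section 10 reports fat-free mass index for the earlier project without naming the method behind it.

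The cost is a few sentences, a standard bootstrap in R (already the named software) and somewhat less favourable reported accuracy. No new patients or measurements are needed, and a real benefit of MUAC is preserved.
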